# 6 Statistical methods for Pharmacokinetic (PK) parameters

VAY736 plasma concentration data will be listed by treatment, subject, and visit/sampling time point. Descriptive summary statistics will be provided by treatment and visit/sampling time point, including the frequency (n, %) of concentrations below the LLOQ and reported as zero. Summary statistics will include mean (arithmetic and geometric), SD, CV (arithmetic and geometric), median, minimum and maximum. Concentrations below LLOQ will be treated as zero in summary statistics. A geometric mean will not be reported if the dataset includes zero values.

Pharmacokinetic parameters will be listed by treatment and subject. Descriptive summary statistics will include mean (arithmetic and geometric), SD, and CV (arithmetic and geometric), median, minimum and maximum. An exception to this is Tmax where median, minimum and maximum will be presented.

Modeling of the PK data may be performed as appropriate. During modeling of the pharmacokinetics of the study drug, the broad principles outlined in the FDA Guidance for Industry: Population Pharmacokinetics will be followed. Subjects with missing PK parameters (e.g., Cmax, AUClast, AUCinf) in some but not all periods will be included in a mixed model

analysis assuming missing at random. This modelling of the PK data will be performed by the Novartis PKist.

PK/PD modeling will be used to explore the relationship between extent and duration of B cell depletion and the pharmacokinetic profile of VAY736. The PK/PD modelling will be performed internally at Novartis. Overlaid individual B cell counts with PK concentrations will be provided by Covance.

## 7 Statistical methods for Pharmacodynamic (PD) parameters

### 7.1 Primary parameter

The primary aim of this study is to evaluate the effect of a single i.v. dose VAY736 on the clinical disease activity of primary Sjögren's syndrome patients as measured by the ESSDAI at Week 12 compared to baseline. The statistical analysis model will include data on the ESSDAI from all timepoints at which it was recorded (baseline, Weeks 6, 12 and 24) but the primary comparison is made for Week 12.

The ESSDAI is an established disease outcome measure for Sjögren's syndrome that will be applied to the study patients at baseline and again at Weeks 6, 12 and 24. The instrument contains 12 organ-specific domains contributing to disease activity. For each domain, features of disease activity are scored in 3 or 4 levels according to their severity. These scores are then summed across the 12 domains in a weighted manner to provide the total score.

It is assumed that the ESSDAI will follow an approximate normal distribution. If, on blinded review of the data, this assumption appears to not be met, alternative statistical methods may be applied, e.g. data may be log transformed with changes from baseline in the log transformed data being analyzed.

A positive sign of therapeutic effects will be considered to be a difference of at least 5 points in the change from baseline between VAY736 and placebo with a moderate level of evidence. Additionally there should be a high level of evidence that is a difference between VAY736 and placebo. The two active doses will be pooled for the primary efficacy analysis (unless there is evidence of inferiority of the 3 mg/kg dose to the 10 mg/kg dose). These criteria will be evaluated by calculating Bayesian posterior probabilities as follows:

```
Pr (\theta_{VAY736,12w}-\theta_{placebo,12w}>0 \mid data) > 90\% and Pr (\theta_{VAY736,12w}-\theta_{placebo,12w}>5 \mid data) > 50\% where \theta means change from baseline in ESSDAI at 12 weeks.
```

It is assumed that  $Y_{ijt}$ , the observed change from baseline in ESSDAI for subject i receiving treatment j (VAY736 or placebo) at time t, follows a normal distribution  $N(\theta_{jt}, \sigma^2)$ , It is further assumed that  $\theta_{jt}$  follows a standard non-informative prior Normal distribution,  $p(\theta_{jt}, \sigma^2) = 1/\sigma^2$ .

The statistical model will be a repeated measures fitting terms for treatment by timepoint and baseline by timepoint using the SAS procedure PROC MCMC. Estimates of the difference between VAY736 and placebo at each timepoint will be derived from this model and presented together with 95% credible intervals. The estimates of the posteriors probabilities of the efficacy criteria being met will be provided.

Patients with missing ESSDAI at baseline will not be included in the analysis. Patients with missing data at one or more timepoints post baseline will be included in the analysis. The planned mixed effects model assumes that missing values are missing at random. The reasonableness of this assumption will be checked during the blinded review of the data and if necessary further methods may be applied.

Summary statistics will be provided for absolute and changes from baseline in ESSDAI by treatment and timepoint. Mean (SD) plots for absolute and changes from baseline in ESSDAI will also be provided. Overlaying individual profiles will also be provided by treatment.

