### 2.2 Study design and treatment

This is a double-blind, randomized, placebo-controlled, parallel-group, non-confirmatory study to assess the safety, tolerability, pharmacokinetics, immunogenicity, pharmacodynamics and clinical efficacy of VAY736 administered intravenously as a single dose in pSS patients. The patients will be enrolled in 2 sequential cohorts:

- 3 mg/kg cohort (Cohort 1): 6 patients randomized to receive a single dose of VAY736 at a starting dose of 3.0 mg/kg or placebo at a 2:1 ratio; approximately 4 patients in this cohort will receive a 3.0 mg/kg dose of VAY736 and approximately 2 patients will receive placebo.
- 10 mg/kg cohort (Cohort 2): 20 patients randomized to receive a single dose of VAY736 at a dose of 10.0 mg/kg or 3.0 mg/kg or placebo at a 6:1:3 ratio, respectively. Around 12 patients will receive 10 mg/kg of VAY736 in this cohort and around 6 will receive placebo. Approximately 2 patients will receive 3.0 mg/kg in this cohort to maintain a level of blinding regarding the dose received.

Between Cohort 1 and Cohort 2 recruitment will be paused and a safety review will be conducted by the VAY736 project team and the principle investigators.

The single doses of 3 - 10 mg/kg are based on the two highest doses safely administered in Part 1 of the SAD phase I study recently completed in RA patients. This study will enroll around 26 patients with primary Sjögren's syndrome. At least 24 subjects are expected to complete the study.

Subjects that are prematurely withdrawn from the study for reasons other than safety will be replaced on a case by case basis. Data from the withdrawn patients will still be used in the primary analysis as much as possible but the sponsor will use replacement patients to obtain complete data on at least 24 patients.

[figure not shown]
At Week 24 the blinding was broken to confirm treatment allocation. Investigators will follow the guidance below:

[figure not shown]
- If a patient received VAY736 and their B cell recovery was demonstrated at Week 24, then patients should have returned for their End of Study visit approximately 4 weeks later.
- Those patients who did not meet the criteria for B cell recovery at Week 24, will return to the site every 8 weeks until Week 52, then after Week 52, every 24 weeks until 2 years post dose (Week 100) and afterwards every 48 weeks, until B cell recovery is demonstrated and the End of Study visit may be scheduled.

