## 4 Interim analyses

Prior to this amended RAP two interim analyses have been performed, firstly when 25 and secondly when all 27 subjects had completed the Week 12 visit in order to assess the effect of VAY736 on the primary endpoints. For these subjects the efficacy endpoints (along with relevant safety data) were examined as a preliminary evaluation of therapeutic effects.

In addition, an interim safety review was performed between Cohort 1 and Cohort 2.

Additional interim analyses may be conducted to support decision making concerning the current clinical study.

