### 7.2 Supportive analyses for the primary parameter

The primary analysis uses a standard mixed model repeated measures approach where timepoints are considered as factors. This was chosen since the time course of ESSDAI changes following a single dose of VAY736 or placebo is not known. Supportive analyses will attempt to model the time effect to better describe changes over time, the model may include the following covariates: baseline, treatment, time, treatment by time interaction, treatment by time square interaction, as well as a random intercept and a random slope for each patient. Time will be modeled as a continuous variable. The model may be simplified if there are problems with convergence. The treatment by time square interaction will be included if it improves the fit.

Potential differences in efficacy between the 3 mg/kg dose and the 10 mg/kg dose of VAY736 may be explored.

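### Section 7.1 lets a blinded review change the primary ESSDAI and missing-data methods although efficacy interims and unblinding are past, and its log-scale example does not fit the 5-point criterion

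*SAP*

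**What the plan says.** Section 7.1 assumes that ESSDAI is approximately normal and then adds: "If, on blinded review of the data, this assumption appears to not be met, alternative statistical methods may be applied". The example given is that "data may be log transformed with changes from baseline in the log transformed data being analyzed". For missing data, the same section assumes missing at random and says: "The reasonableness of this assumption will be checked during the blinded review of the data and if necessary further methods may be applied". Those further methods are not named.

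The efficacy rule, also in 7.1, looks for "a difference of at least 5 points in the change from baseline between VAY736 and placebo". It is put as two posterior conditions, Pr(difference > 0) > 90% and Pr(difference > 5) > 50%, with theta defined as the change from baseline in ESSDAI at 12 weeks.

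On timing, section 4 states that "two interim analyses have been performed, firstly when 25 and secondly when all 27 subjects had completed the Week 12 visit", and that efficacy endpoints were examined at those interims. Section 2.2 states: "At Week 24 the blinding was broken to confirm treatment allocation". Section 7.4 drops the Kaplan-Meier and log-rank analyses because the earlier interims had shown no B cell depletion on placebo. Section 1.2 gives a change in statistical model as an example of a minor change, which may be captured in a note to file, a RAP addendum or the CSR.

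**The concern.** A blinded review protects a data-driven choice of method only if those who choose do not know the results by arm. This version of the RAP was written after the Week 12 efficacy data had been examined twice, and its authors knew at least some results by arm. The trigger in 7.1 therefore depends on a condition that a new review could no longer credibly meet. Section 1.2 adds to this, since a change to the primary model would not need a new RAP version.

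The one alternative that 7.1 describes raises a second problem. It moves the analysis to a scale on which the 5-point threshold has no fixed meaning. If it were used now, a replacement threshold or a back-transformation rule would have to be chosen after the Week 12 results had been seen. The two posterior conditions are the plan's only stated rule for a positive sign of efficacy, so the credibility of that decision is at stake.

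**Working it through.** **Timing.** The relevant statements, side by side:

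- Section 7.1: the primary method and the missing-data method may change on a blinded review.
- Section 4: before this version, two interims assessed the effect on the primary endpoints, the second with all 27 subjects past Week 12.
- Section 2.2: the blind was broken at Week 24.
- Section 4.1: the last Week 52 visit is dated 05Oct2016. The primary model uses ESSDAI "from all timepoints at which it was recorded (baseline, Weeks 6, 12 and 24) but the primary comparison is made for Week 12", so all of its data come before Week 52.
- Section 7.4: interim results by arm had already led to a change of analysis in this version.

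Together these mean that a review held from this version onwards could not credibly be blinded for Week 12 ESSDAI. The SAP records no outcome of any review held before the first interim.

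**Scale.** The SAP gives no baseline mean ESSDAI, so the baselines b and the placebo fall d below are assumptions. The criterion is read as 5 points in favour of VAY736, that is, a 5-point larger fall.

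On the log scale the treatment effect is a log ratio. A threshold of 5 carried over literally would be a ratio of exp(5) = 148, or exp(-5) = 0.0067, which cannot be meant.

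The ratio that matches a 5-point larger fall is (b - d - 5)/(b - d):

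| Baseline b | d = 0 | d = 2 |
|---|---|---|
| 10 | 5/10 = 0.50 | 3/8 = 0.38 |
| 15 | 10/15 = 0.67 | 8/13 = 0.62 |
| 20 | 15/20 = 0.75 | 13/18 = 0.72 |

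Conversely, with placebo unchanged, a fixed ratio r means b(1 - r) points:

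| Ratio r | b = 10 | b = 20 |
|---|---|---|
| 0.50 | 5.0 | 10.0 |
| 0.67 (2/3) | 3.3 | 6.7 |
| 0.75 | 2.5 | 5.0 |

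So no single log margin reproduces the 5-point threshold. A margin chosen between 0.50 and 0.75 would mean anything from 2.5 to 5 points at baseline 10, and from 5 to 10 points at baseline 20. The condition on a difference above zero does carry over in direction, since a ratio of 1 means no difference. Only the 5-point condition is affected.

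**The case against.** The strongest reply is that this is stale wording with no consequence. The RAP uses the future tense elsewhere for past events: section 2.2 still describes an interim as planned and the pause between cohorts as to come, although section 4 reports both interims and the safety review as done. Read literally, 7.1 permits a change only on a blinded review. If that is no longer possible, the clause has lapsed and the stated model is the default. A review may also have been held before the first interim and recorded in a note to file or addendum that is not at hand.

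Much of this stands. A reader might infer that an unblinded review is pending, that no blinded review was ever held, or that the method was switched after the results were known. The documents support none of these. A reader might also see a conflict with section 7.2, which says: "The primary analysis uses a standard mixed model repeated measures approach where timepoints are considered as factors". That sentence contrasts timepoints as factors with continuous time in the supportive model. It says nothing about scale, so it neither conflicts with 7.1 nor settles the question.

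On scale, the log transformation is only an example. The model is fitted by MCMC with baseline terms, so posterior draws could be back-transformed and judged in points. That is possible, but it needs a reference baseline, and the plan names none.

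The reply does not remove the defect. A lapsed clause left in force invites dispute over whether the model is final, and section 1.2 does not exempt the primary model from its minor-change route.

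**Conclusion.** The point holds in limited form. The plan leaves its primary method and missing-data method open to change on a review that, if held from now on, could not credibly be blinded. Its change-control rule would let a change of model be recorded as minor. The only alternative it describes does not fit its own 5-point condition: 5 points corresponds to ratios from 0.50 to 0.75 over assumed baselines of 10 to 20 with placebo unchanged, and from 0.38 to 0.72 if placebo falls by an assumed 2 points.

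The scale finding does not depend on the particular baselines chosen, only on their not all being equal. The timing finding rests on the RAP's own chronology and on the use of interim results by arm in section 7.4. No effect on the trial's decision is claimed. As the study is non-confirmatory, the importance is low to moderate, and the gain is in the credibility of the efficacy decision.

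**What to change.** In section 7.1:

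- Delete the blinded-review trigger in both places, for normality and for missing data. If a review before the first interim is documented, record its decision instead.
- Fix the repeated-measures model on the ESSDAI points scale as the primary analysis, and judge both posterior conditions on that scale only.
- Report any log-scale or alternative missing-data analysis as a sensitivity analysis. Give log-scale effects as ratios, state a rule for zero scores (whose logarithm is undefined), and do not apply the 5-point rule to them.

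In section 1.2, class any change to the primary-endpoint model or its missing-data method as major and version-controlled.

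The cost is wording only, with no new data. The small downside is less freedom to change the headline model if normality looks poor, but the alternative would still be reported.

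### The primary Bayesian success rule points the wrong way: as written it is met when the estimated ESSDAI change on VAY736 is worse than on placebo by more than 5 points

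*SAP*

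**What the plan says.** Everything needed is in SAP Section 7.1.

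- **Scale.** Within each domain, "features of disease activity are scored in 3 or 4 levels according to their severity". The total follows: "These scores are then summed across the 12 domains in a weighted manner to provide the total score".
- **Parameter.** The section states that "\theta means change from baseline in ESSDAI at 12 weeks". The modelled outcome is defined in the same way, as "the observed change from baseline in ESSDAI for subject i receiving treatment j (VAY736 or placebo) at time t".
- **Intent.** A sign of therapeutic effect is a "difference of at least 5 points in the change from baseline between VAY736 and placebo", held with moderate evidence, together with strong evidence of some difference. Neither part of that sentence gives a direction.
- **Rule.** The two conditions are "Pr (\theta_{VAY736,12w}-\theta_{placebo,12w}>0 \mid data) > 90"% and "Pr (\theta_{VAY736,12w}-\theta_{placebo,12w}>5 \mid data) > 50"%.

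The section then adds a non-informative prior and a repeated-measures model in PROC MCMC, and it commits to reporting the posterior probabilities for these criteria.

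**The concern.** On a scale where more severe activity scores higher, an effective drug lowers the score more than placebo does. With change taken in its ordinary sense (Week 12 minus baseline), benefit makes VAY736 minus placebo negative. Both conditions require that contrast to be positive, so the formula contradicts the purpose stated for it.

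This is the only numerical success rule the SAP gives for the primary efficacy endpoint. A programmer who follows it literally would report the probability of harm under an efficacy label. An effective drug would fail the rule and a harmful one could pass. Both inequalities share the contrast and the direction, so neither would expose an error in the other.

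**Working it through.** **Step 1: direction, from the text alone.**

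- Higher ESSDAI means more disease activity, because domains are scored by severity and summed with weights (Section 7.1).
- Theta is change from baseline (Section 7.1), with no mention of baseline minus Week 12, reduction or improvement.
- The rest of Section 7.1 speaks of absolute values and changes from baseline and does not redefine the sign of the difference.
- Where the SAP means a fall, it says so: in Section 7.4, De Vita responders are defined by a reduction from baseline.

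So benefit means theta(VAY736) − theta(placebo) < 0, while the rule asks for > 0 and > 5.

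**Step 2: size, as an illustration.** The SAP gives no SD, power or operating characteristics, so there is no stated figure to reproduce.

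Inputs:

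- Planned allocation (Section 2.2): VAY736 4 + 2 + 12 = 18, with both doses pooled as Section 7.1 provides; placebo 2 + 6 = 8; total 26.
- Prior proportional to 1/σ² (Section 7.1).
- SD of the Week 12 change: assumed 6, range 4 to 10.
- Simplification: Week 12 only, without the baseline covariate or the repeated measures.

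Under this prior the posterior of the difference is a t distribution with 18 + 8 − 2 = 24 degrees of freedom, centred at the observed difference d, with scale s × √(1/18 + 1/8) = 0.425 s.

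- Condition 2 (> 5 with probability > 50%) holds when d > 5.
- Condition 1 (> 0 with probability > 90%) holds when d > t(0.90, 24) × 0.425 s = 1.318 × 0.425 s. That is 3.4 at s = 6 and 5.6 at s = 10.

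Posterior probabilities at s = 6 (scale 2.55):

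| Observed VAY736 − placebo | Pr(> 0) | Pr(> 5) | Rule as written |
|---|---|---|---|
| −10 (large benefit) | 0.0003 | < 0.0001 | not met |
| −5 (benefit) | 0.031 | 0.0003 | not met |
| +10 (large harm) | 0.9997 | 0.969 | met |

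Probability of meeting the rule over repeated trials, allowing for sampling variation in both d and s:

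| True VAY736 − placebo | SD 4 | SD 6 | SD 8 | SD 10 |
|---|---|---|---|---|
| −8 (better) | < 0.001 | < 0.001 | < 0.001 | < 0.001 |
| −5 (better) | 2e-9 | 0.00004 | 0.0015 | 0.0065 |
| 0 | 0.002 | 0.025 | 0.068 | 0.094 |
| +5 (worse) | 0.50 | 0.50 | 0.49 | 0.44 |
| +8 (worse) | 0.96 | 0.88 | 0.81 | 0.71 |

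**Step 3: the rule reversed.** By symmetry, the reversed rule has the same table with the sign of the true difference switched. A true 8-point benefit then succeeds with probability 0.96, 0.88, 0.81 and 0.71 for SD 4, 6, 8 and 10. A true 5-point benefit succeeds about half the time (0.44 at SD 10).

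**The case against.** The strongest reply is that nobody could misread the intent. Section 7.1 speaks of therapeutic effects and of efficacy criteria, so theta must have been meant as improvement. The direction of a derived variable may be fixed in the programming specifications (Module 8), which are not shown. The SAP also requires estimated differences with credible intervals, summary tables and profile plots, so a reversed conclusion would be noticed. The study is non-confirmatory, and nothing shown suggests that the interim analyses were read backwards.

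Much of this is fair. The intent was very probably benefit, and this is best called a slip in the formula, not a deliberate choice. Whether the code is also wrong cannot be known from the SAP. The operating characteristics only illustrate: they rest on an assumed SD, a simplified model and the planned 26 patients, whereas Section 4 reports 27. The rule also concerns the posterior estimate, not the true effect: as the table shows, a drug with no effect can sometimes meet it.

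None of that makes the written rule right. The methodology module exists to fix the direction in advance, and it states a definition of theta under which both inequalities are wrong. The prose does not rescue it, because it speaks only of a difference without a sign. A reader has to override the written definition to reach the intended rule.

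**Conclusion.** The point holds and must be fixed. With theta as the SAP defines it, success requires the posterior median of VAY736 minus placebo to exceed +5 and at least a 90% probability that VAY736 is worse. This conclusion rests only on the ordinary meaning of change from baseline and on the SAP's own description of the scale. It does not depend on the assumed SD, the sample size or the simplified model; those affect only the probabilities in the tables. The rule would be correct only if theta meant baseline minus Week 12, which the SAP nowhere states.

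**What to change.** Reverse both contrasts in Section 7.1:

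- Pr(θ_placebo,12w − θ_VAY736,12w > 0 | data) > 90%, and
- Pr(θ_placebo,12w − θ_VAY736,12w > 5 | data) > 50%.

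Writing VAY736 minus placebo < 0 and < −5 is equivalent. Keeping the inequalities and defining theta explicitly as reduction from baseline would also work. Whichever form is chosen, state how change is calculated and which sign means improvement, and give the 5-point difference a direction in the prose.

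Then confirm that the PROC MCMC program, the Module 7 shells and the Module 8 derivations use the same direction, and check how the two completed interim analyses (Section 4) coded it. The cost is a line or two of SAP text under version control and a code check. No patients or data are affected.
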